3. OBJECTIVES

3.1 Primary Objective

The study will test the hypothesis that ESRD patients, who are at least 50 years of age and beginning hemodialysis (either scheduled for their first session or within two months of the initial treatment), will experience a 60% relative risk reduction in SCD mortality through WCD use as measured at six calendar months after randomization. The primary objective will be evaluated using intention-to-treat analysis.

WCD therapies are anticipated to reduce the risk of SCD by 60% over the course of use, similar to other personal defibrillation therapies such as ICDs. The hypothesized relative reduction in SCD translates to a 2.1% absolute reduction in the risk of SCD mortality over 6 months of follow-up, given that the SCD rate during that period is expected to be 3.5%. The hypothesized 60% reduction in SCD is also expected to result in a 15% reduction in total mortality over 6 months for this patient group, a consequence that would be of major clinical importance.

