7. STUDY DESIGN

This study will employ a group sequential two-arm randomized clinical trial to test the hypothesis that the wearable cardioverter defibrillator (WCD) reduces overall mortality within a 6 calendar month period beginning at the time of randomization, which is to occur no later than 2 calendar months after the initiation of hemodialysis.

Enrolled subjects will be 1:1 randomized to WCD or non-WCD, stratified by enrolling site and, implicitly, by calendar time of enrollment. All subjects will be followed for at least 6 calendar months regardless of compliance. The primary endpoint is the binary event of whether or not sudden cardiac death occurs within the 6 month follow-up period. The primary analysis will be an intention-to-treat analysis based on the randomization, ignoring the fact that some subjects randomized to WCD may discontinue use of the device early while some subjects randomized to the non-WCD arm may obtain and wear a WCD.

Overall mortality at 6 calendar months in the non-WCD arm is expected to be 14%, with one quarter of all deaths due to sudden cardiac death (SCD rate of 3.5%).² Taking some anticipated noncompliance into consideration, as some subjects are expected to discontinue WCD prior to 6 months, we hypothesize that the WCD will provide a relative reduction in SCD of 60%. Thus, we

expect an absolute reduction of 2.1% in SCD mortality, corresponding to a relative risk (RR) of 0.40 and an odds ratio (OR) of 0.39.

The exact number of subjects to be randomized is uncertain since the group sequential trial was designed to have 46% power to stop at the first interim look at 650 (50%) subjects per arm, and 69% power to stop at the second interim look at 975 (75%) subjects per arm, while controlling the overall significance level at $\alpha = 0.05$. But if the study continues to the third and final look, a maximum of 1,300 subjects will be enrolled in each arm, for a total of 2,600 subjects providing 91% power to detect the hypothesized 60% relative reduction in overall 6-month SCD mortality from 3.5% down to 1.4%.

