7.1 Endpoint Assessment

A Mortality Committee will provide an assessment regarding mortality events with a categorization of the death based on underlying cause and mechanism of death. All deaths will be adjudicated by the Mortality Committee and classified as 'sudden (SCD)', 'not sudden' or 'indeterminate'. In addition, the death will be classified as 'cardiac', and 'non-cardiac'. All deaths will be used as endpoints in the primary analysis and the adjudicated results used as endpoints in the secondary analyses.

This committee will be blinded to information regarding the use of a WCD. The death reports from enrolling sites will be transcribed by an unblinded individual and provided in a uniform format to the adjudication committee. Transcribed notes will be redacted of information regarding WCD or WCD therapy to maintain the blinding of the committee. The Mortality Committee will not utilize WCD or AED interrogation information when classifying death as cardiac or non-cardiac, and as sudden or non-sudden.

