7.2 Statistical Methods

The primary analysis will be based on a 1-df likelihood ratio test (LRT) of the null hypothesis that the 6 calendar month SCD mortality rate is identical for subjects randomized to WCD versus non-WCD (i.e. odds ratio of 1), conditional on enrolling site and date of enrollment (stratification variables that define randomized blocks), and further

parametrically adjusted for five additional pre-specified risk factors via conditional logistic regression (CLR):

- age (continuous, and flexibly modeled via a 4-df continuous piecewise linear spline with knots at 60, 70, and 80 years of age, allowing for a separate odds ratio per year within each decade of age),
- ejection fraction (continuous, and modeled via a 2-df continuous piecewise linear spline with a knot at 50%, allowing for a separate odds ratio per year above and below 50%, given that it is expected that mortality risk likely decreases smoothly up to about 50% but then perhaps levels off thereafter),
- race/ethnicity (binary: white non-Hispanics versus all others),
- diabetes (binary: yes versus no),
- myocardial infarction (binary: yes versus none),
- dialysis access (binary: catheter versus no catheter).

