The adjusted odds ratio (OR) for WCD along with its corresponding 95% confidence interval (CI) will be estimated via CLR. Note that, in stark contrast to case-control studies, there is essentially no loss of efficiency due to heavy stratification resulting in a large number of strata, provided almost every stratum contains at least 1 patient from each group (WCD, non-WCD). This condition is guaranteed, given the plan to stratify on only those variables defining blocks for randomization. This was verified by simulation and supported by results in DeStavola and Cox, which states that there is no loss of efficiency if the strata are perfectly balanced (e.g. via stratified randomization).³⁹ Thus, there is no concern of “over-stratifying,” even if SCD were independent of enrolling site and date of enrollment. In fact, in order for CLR to be computationally feasible it is necessary that no stratum be too large. Furthermore, even if SCD were independent of some or all of the 5 variables (8 df) parametrically adjusted for, the loss of efficiency and precision would be negligible since randomized treatment is completely independent of all risk factors. On the other hand, to the extent that SCD is associated with any of the adjustment or stratification variables, failing to control for them at the analysis stage could result in a substantial loss of efficiency. Standard power calculations assume that subjects are independent and identically distributed, at least given the adjustments, but this assumption would be violated if important predictors of SCD were not controlled for, thus resulting in lower power than that suggested by standard sample size and power calculations.

Exploratory analysis of the secondary endpoint of all-cause mortality will be based on a single 2-sided nominal 0.05 level LRT, using the same CLR method as used to analyze SCD, with whatever sample size (650, 975, or 1300 patients per arm) happens to be available when the trial ends. A simple nominal 0.05 level test will be performed for the analysis of all-cause mortality, treating the resulting data as a fixed sample size.

Secondary analyses will test interactions between WCD and SCD risk factors in order to investigate whether there are subgroups for whom WCD might be especially effective. Interactions between pairs of SCD risk factors will also be explored in secondary analyses.

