7.3 Group Sequential Design

Standard group sequential methods³⁸ can be applied, given the large-sample approximate normality of the estimated log(OR), and PASS 11 software was used to compute the alpha and power values for our custom group sequential stopping rule. We plan to conduct 2

interim analyses once the 6 calendar month SCD outcome has been observed for 1/2 and 3/4 of the subjects. Our custom stopping boundaries retain 4% nominal alpha for the third and final look, provided the study doesn't stop early, while testing each of the 2 interim analyses at the nominal alpha level of 0.01375 (see Table 4). The overall alpha level for the study is .05.

Table 4: Group sequential design for the two-arm randomized clinical trial.

Look	Relative Information	# WCD subjects	# non-WCD subjects	# Total subjects	Nominal Alpha	Corrected Alpha
1	50%	650	650	1,300	0.01375	0.01375
2	75%	975	975	1,950	0.01375	0.02231
3	100%	1,300	1,300	2,600	0.04000	0.05000

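### The protocol names two primary endpoints, SCD in most sections and all deaths in Section 7.1; the stated 91% power is for SCD, and all deaths would have about 34%

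*Combined protocol and SAP*

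**What the plan says.** Most of the document makes SCD within six calendar months the primary endpoint:

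- Section 3.1 (Primary Objective): patients "will experience a 60% relative risk reduction in SCD mortality through WCD use as measured at six calendar months after randomization".
- Section 7, second paragraph: "The primary endpoint is the binary event of whether or not sudden cardiac death occurs within the 6 month follow-up period".
- Section 7.2: the null hypothesis of the primary test is that "the 6 calendar month SCD mortality rate is identical for subjects randomized to WCD versus non-WCD".
- Section 7.3 times the interim looks by the observed six-month SCD outcome, and Sections 7 and 7.4 give 91% power for SCD of 3.5% versus 1.4%.
- Section 3.2.1 lists total mortality as a secondary objective, and Section 7.2 says: "Exploratory analysis of the secondary endpoint of all-cause mortality will be based on a single 2-sided nominal 0.05 level LRT".

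Two places say otherwise:

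- Section 7.1: "All deaths will be used as endpoints in the primary analysis and the adjudicated results used as endpoints in the secondary analyses".
- Section 7, opening sentence: the trial is designed "to test the hypothesis that the wearable cardioverter defibrillator (WCD) reduces overall mortality within a 6 calendar month period".

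**The concern.** The Section 7.1 sentence cannot be read as compatible with the rest. The same section has the Mortality Committee class every death as sudden, not sudden or indeterminate, so SCD exists only as an adjudicated result. Taken literally, Section 7.1 moves SCD to the secondary analyses and puts all deaths in its place. Nor can the sentence just mean that every death is reviewed, because the section has already said that separately.

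Three things are at stake.

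- **Error control.** Section 7.3 states "The overall alpha level for the study is .05", and the boundaries spend that alpha on one endpoint. All-cause mortality gets a single nominal 0.05 test outside the sequential correction. With two candidate primaries on paper, the choice could be argued after results are known.
- **Interim conduct.** Section 13 has the DSMB validate the events that feed the stopping rule. Sections 7.1 and 7.3 imply different sets of events.
- **Possible divergence.** Under Section 7.1.1, a death more than one hour after an arrest from a ventricular arrhythmia is non-sudden. A device that only delayed such deaths past one hour would lower SCD without lowering total mortality.

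**Working it through.** **Inputs from the document**

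- Table 4: looks at 50%, 75% and 100% information; two-sided nominal alphas 0.01375, 0.01375 and 0.04; maximum 1,300 per arm.
- SCD: 3.5% control, 1.4% WCD (Sections 7 and 7.4).
- All deaths: 14% control (Section 7), and the same absolute reduction of 2.1 points (Section 3.2.1), giving 14.0 − 2.1 = 11.9% in the WCD arm.

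**Method.** Critical values are z = Φ⁻¹(1 − α/2): 2.464, 2.464 and 2.054. The drift at full information is

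θ = ln(OR) / SE, with SE² = 1/(n·p₁·(1−p₁)) + 1/(n·p₂·(1−p₂)) and n = 1,300.

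At information fraction t the test statistic has mean θ√t, and its correlation between fractions s < t is √(s/t). Cumulative crossing probabilities come from 8 million simulated draws. No covariate or stratum adjustment is made.

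**Step 1: reproduce the plan's own figures**

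- Under the null, cumulative alpha is 0.0138, 0.0223 and 0.0499. Table 4 gives 0.01375, 0.02231 and 0.05.
- For SCD, ln(OR) = 0.9378 and SE² = 0.02278 + 0.05573 = 0.07850, so SE = 0.2802 and θ = 3.347.
- At look 1, Φ(3.347 × √0.5 − 2.464) = Φ(−0.097) = 46.1%.
- All three looks give 46.1%, 69.4% and 90.8%, matching the stated 46%, 69% and 91%.

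**Step 2: same boundaries, all deaths**

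- ln(OR) = 0.1866 and SE² = 0.006389 + 0.007337 = 0.013726, so SE = 0.1172 and θ = 1.593.
- At look 1, Φ(1.593 × √0.5 − 2.464) = Φ(−1.337) = 9.1%.

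| Cumulative power | Look 1 | Look 2 | Look 3 |
|---|---|---|---|
| SCD, 3.5% vs 1.4% | 46.1% | 69.4% | 90.8% |
| All deaths, 14.0% vs 11.9% | 9.1% | 16.5% | 34.2% |

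**Step 3: why it falls.** The expected difference in events is the same: 45.5 versus 18.2 SCDs and 182 versus 154.7 deaths, 27.3 in each case. The noise is larger. The unpooled standard error of the risk difference is √[(0.035×0.965 + 0.014×0.986)/1,300] = 0.605 points for SCD, and √[(0.14×0.86 + 0.119×0.881)/1,300] = 1.316 points for all deaths. The standardised effect drops from 2.1/0.605 = 3.47 to 2.1/1.316 = 1.60.

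**Step 4: sensitivity to the formula.** Pooled and unpooled difference-in-proportions drifts also give 34.2% for all deaths. A fixed test at 1,300 per arm gives 35.7% at two-sided 0.05 and 32.3% at 0.04. A fixed two-sided 0.05 test with 91% power on all deaths would need about 5,570 per arm.

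**The case against.** The best reply is that the intent is plain. The protocol summary, primary objective, endpoint statement, null hypothesis, interim timing and power table all concern SCD. No boundary or sample size exists for all deaths, and Section 7.2 calls that analysis exploratory. On this view the Section 7.1 sentence is an outlier, the opening of Section 7 states a hypothesis loosely rather than defining an endpoint, and 91% was never claimed for all deaths. The documents also contain no rule giving Section 7.1 precedence.

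Much of this stands. The 91% is correct for the endpoint it was calculated for, the 34% is conditional on following Section 7.1, and the weight of the text favours SCD. The opening sentence of Section 7 is weaker evidence than Section 7.1.

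That does not remove the conflict. The Section 7.1 sentence is current text that expressly assigns endpoints to the primary and secondary analyses, and nothing elsewhere reconciles it. A primary endpoint should not have to be inferred by counting sections.

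One further point stands. Simply naming deaths classed as SCD as primary would silently make indeterminate deaths non-events, so the correction should address them.

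**Conclusion.** The concern holds: the plan is wrong as written, because it gives contradictory primary endpoints. This is an inconsistency in the text, not an error in the sample size for SCD, where the 91% is reproduced.

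If all deaths were primary, power at the maximum sample size would be about 34% (32% to 36% across standard calculations). That rests on the protocol's own assumptions of 14% control mortality and a 2.1-point reduction, in which every SCD prevented is a death prevented within six months. If some of those patients died of other causes in that time, power would be lower still. The document states no power for all-cause mortality.

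It must be fixed, since it concerns the trial's central claim and the endpoint to which the alpha is attached.

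**What to change.** Change two sentences to match the endpoint the design was sized for.

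1. **Section 7.1.** Replace the sentence on endpoints with: *Death within 6 calendar months of randomization that the blinded Mortality Committee classifies as SCD is the primary endpoint. Death from any cause in the same period is a secondary endpoint.*
2. **Section 7, opening sentence.** Replace overall mortality with SCD mortality.

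In the same edit, state in Section 7.1 how deaths classed as indeterminate enter the primary analysis, and make clear that the events the DSMB validates for the stopping rule are these primary endpoint events.

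The cost is a wording amendment. Sample size, boundaries, power table and data collection do not change. It should be made before any unblinded interim look, so that the choice cannot be influenced by results.

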7.1.1 SCD definitions

For witnessed deaths, sudden cardiac death (SCD) will be defined as an unexpected, non-traumatic, non-self-inflicted fatality in otherwise stable subjects who die within one hour of the onset of the terminal symptoms (and for whom dialysis-noncompliance or withdrawal have been excluded). Subjects dying more than one hour after a sudden cardiac arrest (SCA) from a ventricular arrhythmia will be designated as non-sudden death due to ventricular arrhythmia.

For unwitnessed deaths, participants will meet the definition of sudden cardiac death if they are found dead within 24 hours of being well, assuming there is no evidence of another cause of death during that time period including dialysis-noncompliance (or withdrawal). Autopsy results may be used when available.

7.1.2 Arrhythmia Adjudication

A separate Wearable Defibrillator Interrogation Adjudication Committee will focus on assessing cardiac arrhythmias triggering WCD therapy regarding its appropriateness and effectiveness. All events will be reviewed by an independent committee and will be categorized as appropriate, inappropriate, or indeterminate. Details of arrhythmic events and related therapy will be recorded.

7.2 Statistical Methods

The primary analysis will be based on a 1-df likelihood ratio test (LRT) of the null hypothesis that the 6 calendar month SCD mortality rate is identical for subjects randomized to WCD versus non-WCD (i.e. odds ratio of 1), conditional on enrolling site and date of enrollment (stratification variables that define randomized blocks), and further

parametrically adjusted for five additional pre-specified risk factors via conditional logistic regression (CLR):

- age (continuous, and flexibly modeled via a 4-df continuous piecewise linear spline with knots at 60, 70, and 80 years of age, allowing for a separate odds ratio per year within each decade of age),
- ejection fraction (continuous, and modeled via a 2-df continuous piecewise linear spline with a knot at 50%, allowing for a separate odds ratio per year above and below 50%, given that it is expected that mortality risk likely decreases smoothly up to about 50% but then perhaps levels off thereafter),
- race/ethnicity (binary: white non-Hispanics versus all others),
- diabetes (binary: yes versus no),
- myocardial infarction (binary: yes versus none),
- dialysis access (binary: catheter versus no catheter).

The adjusted odds ratio (OR) for WCD along with its corresponding 95% confidence interval (CI) will be estimated via CLR. Note that, in stark contrast to case-control studies, there is essentially no loss of efficiency due to heavy stratification resulting in a large number of strata, provided almost every stratum contains at least 1 patient from each group (WCD, non-WCD). This condition is guaranteed, given the plan to stratify on only those variables defining blocks for randomization. This was verified by simulation and supported by results in DeStavola and Cox, which states that there is no loss of efficiency if the strata are perfectly balanced (e.g. via stratified randomization).³⁹ Thus, there is no concern of “over-stratifying,” even if SCD were independent of enrolling site and date of enrollment. In fact, in order for CLR to be computationally feasible it is necessary that no stratum be too large. Furthermore, even if SCD were independent of some or all of the 5 variables (8 df) parametrically adjusted for, the loss of efficiency and precision would be negligible since randomized treatment is completely independent of all risk factors. On the other hand, to the extent that SCD is associated with any of the adjustment or stratification variables, failing to control for them at the analysis stage could result in a substantial loss of efficiency. Standard power calculations assume that subjects are independent and identically distributed, at least given the adjustments, but this assumption would be violated if important predictors of SCD were not controlled for, thus resulting in lower power than that suggested by standard sample size and power calculations.

Exploratory analysis of the secondary endpoint of all-cause mortality will be based on a single 2-sided nominal 0.05 level LRT, using the same CLR method as used to analyze SCD, with whatever sample size (650, 975, or 1300 patients per arm) happens to be available when the trial ends. A simple nominal 0.05 level test will be performed for the analysis of all-cause mortality, treating the resulting data as a fixed sample size.

Secondary analyses will test interactions between WCD and SCD risk factors in order to investigate whether there are subgroups for whom WCD might be especially effective. Interactions between pairs of SCD risk factors will also be explored in secondary analyses.

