5. STUDY SIZE

A minimum of 1,300 and a maximum of 2,600 subjects will be enrolled into this study. A maximum of 200 sites will enroll patients into the trial.

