7.5 Randomization Scheme

Enrolled subjects will be 1:1 randomized to WCD or non-WCD, stratified by enrolling site and, implicitly, by calendar time of enrollment given the prospective nature of the study. That is, each enrolling site will have its own randomization sequence, ensuring treatment balance within each enrolling site. Each such randomization sequence will consist of a string of random 4- and 6-blocks. That is, there will be a 50% chance that the first block will consist of 4 subjects (2 WCD + 2 non-WCD, in random order), and a 50% chance that it will contain 6 subjects (3 WCD + 3 non-WCD, in random order). Each subsequent block size will similarly be randomly selected. This procedure makes it very difficult for anyone to predict whether the next treatment assignment will be WCD or non-WCD, helping to ensure integrity of the study. In contrast, if each block were of size 4, then it would be trivial to perfectly predict every 4th treatment assignment (as well as the 3rd, if the first two were both WCD, or both non-WCD) which would be undesirable. Using such small blocks will also guarantee near perfect balance no matter where the sequence is truncated, i.e. regardless of how many subjects are enrolled in each site, and it will further guarantee temporal balance not only overall but also within each enrolling site (i.e. balanced treatment x time interaction strata) since each randomization block will contain an equal number of WCD and non-WCD subjects, with the possible exception of the last (incomplete) block in each enrolling site.

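### Section 7.2 calls two-arm strata guaranteed, but incomplete last blocks at sites break that condition and cost a small, unstated amount of information, most at the first look (minor)

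*Combined protocol and SAP*

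**What the plan says.** Section 7.2 makes the primary test "conditional on enrolling site and date of enrollment (stratification variables that define randomized blocks", so the CLR strata are the blocks themselves. It states that heavy stratification costs essentially nothing, "provided almost every stratum contains at least 1 patient from each group (WCD, non-WCD", and then says "This condition is guaranteed, given the plan to stratify on only those variables defining blocks for randomization". It adds that this was checked by simulation, and cites theory that it describes as covering perfectly balanced strata.

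Section 7.5 gives every site its own sequence: "Each such randomization sequence will consist of a string of random 4- and 6-blocks", with the two sizes equally likely. It says that each block is balanced, "with the possible exception of the last (incomplete) block in each enrolling site".

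Section 5 sets the site limit: "A maximum of 200 sites will enroll patients into the trial". Section 7 sets the size: "a maximum of 1,300 subjects will be enrolled in each arm, for a total of 2,600 subjects". Table 4 puts the looks at 1,300, 1,950 and 2,600 subjects in total. Section 7.4 gives cumulative power of 46%, 69% and 91% for SCD rates of 3.5% and 1.4%.

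**The concern.** The exception admitted in Section 7.5 is not carried into Section 7.2. A stratum that holds one arm only contributes nothing to a conditional likelihood, and any SCD in it is lost to the test. A two-arm stratum that is unbalanced contributes less than its size suggests. Section 7.2 gives no rule for such strata, no count of them and no power allowance.

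The number of truncated blocks depends on the number of sites, not of subjects, so the relative loss is largest at look 1. At 200 sites the average is 1,300/200 = 6.5 subjects per site at look 1 and 2,600/200 = 13 at look 3. Section 7.4 relies on a 46% chance of stopping at that first look.

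**Working it through.** **1. Reproduce the plan's power.** Inputs are rates of 3.5% and 1.4%, 650/975/1,300 per arm, and two-sided nominal levels 0.01375, 0.01375 and 0.04 (Sections 7.3, 7.4 and 7.6).

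- ln(OR) = ln[(0.014 × 0.965)/(0.035 × 0.986)] = −0.938.
- Variance × n per arm = 1/(0.035 × 0.965) + 1/(0.014 × 0.986) = 102.05.
- Expected z = 0.938 × √(n/102.05) = 2.367, 2.899, 3.347. Critical values are 2.464, 2.464, 2.054.
- With multivariate normal probabilities at information 0.5/0.75/1, cumulative power is 46.1/69.4/90.8% and cumulative alpha is 0.01375/0.02231/0.0500. Both match the plan.

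**2. Where a site's sequence is cut.** For a cut at an arbitrary point in a sequence of random 4- and 6-blocks, let k be the number of subjects in the open block. k = 0 means that the last block is complete.

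| k | 0 | 1 | 2 | 3 | 4 | 5 |
|---|---|---|---|---|---|---|
| P(k) | 0.2 | 0.2 | 0.2 | 0.2 | 0.1 | 0.1 |
| P(one arm only, given k) | – | 1 | 11/30 | 1/20 | 0 | 0 |

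- Incomplete last block: 1 − 0.2 = 80% of sites.
- One-arm last block: 0.2 + 0.2 × 11/30 + 0.2 × 1/20 = 28.3% of sites.
- Subjects in one-arm strata per site: 0.2 + 2(0.2)(11/30) + 3(0.2)(1/20) = 0.377.

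This gives about 75 subjects at 200 sites, 38 at 100 and 19 at 50. At 200 sites, 75 is 5.8/3.9/2.9% of the subjects at looks 1/2/3. Expected SCDs in these strata at 200 sites: 75 × (0.035 + 0.014)/2 = about 1.8, of 31.8 at look 1 and 63.7 at look 3.

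**3. Share of strata affected.** In simulated enrolment at 200 sites with random site sizes, about 57 strata are one-armed: of 344 at look 1 (16%), 473 at look 2 (12%) and 604 at look 3 (9%). At 100 sites the shares are about 9%, 7% and 5%.

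**4. Total information loss.** With rare events, a stratum of a WCD and b control subjects carries information proportional to ab/(a+b), against (a+b)/4 if balanced. The mean shortfall by position in the block is:

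- 4-block (k = 0 to 3): 0, 1/4, 1/6, 1/12, which average 0.125;
- 6-block (k = 0 to 5): 0, 1/4, 1/5, 3/20, 1/10, 1/20, which average 0.125.

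So the loss is 0.125 × 4 = half a subject per site at every look. At 200 sites that is 100 subjects: 7.7% of 1,300, 5.1% of 1,950 and 3.8% of 2,600. At 100 sites the losses are half of these. A separate simulation of the block-conditional score test kept 92% of the unstratified information at look 1 and 96% at look 3.

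**5. Effect on power, log(OR) approximation.** At 200 sites the effective size per arm is 600/925/1,250, so expected z is 2.274/2.823/3.282.

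| Sites | Look 1 | Look 2 | Look 3 |
|---|---|---|---|
| Plan, no loss | 46.1% | 69.4% | 90.8% |
| 100 | 44.3% | 68.1% | 90.2% |
| 200 | 42.5% | 66.7% | 89.7% |

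**6. Effect on power, simulated CLR likelihood ratio test** (200 equal-rate sites, no covariates, 4,500 trials, Monte Carlo standard error up to about 0.75 points), cumulative rejection:

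| Strata | Look 1 | Look 2 | Look 3 |
|---|---|---|---|
| Blocks as planned | 47.4% | 71.9% | 93.0% |
| Last incomplete block merged | 49.3% | 74.4% | 93.5% |

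The two methods differ in level because the log(OR) formula is the more cautious: for 91% power in a fixed design it needs 1,264 per arm, against 1,179 for a pooled test of proportions (the plan states 1,250). They agree that the loss is small and greatest at the interim looks.

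**The case against.** The case for leaving the text alone has real weight.

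- **The condition says almost every stratum, not every stratum.** Section 7.5 also names the exception openly, so the two sections can be read together. This stands in part. At 50 or 100 sites the condition is close to met. At 200 sites and look 1, with about 16% of strata one-armed, it is hard to call it met, still less guaranteed.
- **200 is a ceiling.** This stands: no expected site number is given, and every loss here scales with the number of sites.
- **Power is not visibly short.** Simulated power with block strata is above 46/69/91% at all three looks. This stands, though that simulation has no covariates and equal-rate sites.
- **Fine strata have a purpose.** Section 7.2 conditions on site and date to protect efficiency if those variables predict SCD, and simulations with equal-rate sites cannot show that benefit. This stands, and it favours merging only the last block over using site alone.
- **Section 7.2 reports its own simulation.** Its details are not in the documents, so whether it truncated blocks is unknown.

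A reader might also infer that randomised subjects are removed from the intention-to-treat analysis. The documents do not support that. Strata that add nothing are inherent to CLR: in the simulation about 89–90% of subjects sit in event-free strata, which are equally silent. Truncation is unrelated to arm, and simulated type I error was similar with block strata and site strata (5.5% and 5.3%, 2,500 trials).

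**Conclusion.** The point holds as a minor one. The two-arm condition is not guaranteed by the design, and the claim of essentially no loss is not accurate at the plan's own site limit. The cost there is about 8/5/4% of information at looks 1/2/3, which on the log(OR) approximation is about 4 power points at look 1 and 1 at look 3. At 100 sites it is half the information loss and about 2 points or less.

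Three stronger readings go too far. Not every site ends on an incomplete block: about one in five ends on a complete one. The figure of 75 is an average at the maximum site count, not an upper limit: the 95% range is about 60 to 94, and nearly equal site sizes give means from 43 to 96 depending on the look. And nothing here shows bias, an intention-to-treat breach or an underpowered trial.

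The result rests on three assumptions: the CLR strata are the actual blocks; each look cuts a site's sequence at an arbitrary point; and the number of sites (50 to 200 shown) and the spread of enrolment across sites, which the documents do not give.

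**What to change.** In Section 7.2, before look 1 and without reference to outcomes:

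1. Specify that at every look each site's last incomplete block is merged with that site's preceding block to form one stratum. Where a site has only one block and it is incomplete, keep it as its own stratum. That second rule is needed: at 200 sites, about 47 to 74 sites would be in this position at look 1, depending on how skewed enrolment is.
2. Replace the sentence about the guarantee, and the no-loss claim, with the expected information loss by look and number of sites.
3. Report, at each look, the subjects and SCDs left in one-arm strata.

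At 200 sites, merging raises look-1 information from about 92% to 95–97% of the unstratified value. The cost is SAP wording and a few lines of code, with no new data and no change to randomisation. The downside is slightly coarser conditioning on enrolment date in the merged stratum.
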